5.3.3.2 Anemia

The primary toxicity of ribavirin is hemolytic anemia, which was observed in approximately 13% of all ribavirin/interferon-treated subjects in clinical trials. Anemia occurs within 1 to 2 weeks of initiation of therapy. Because the initial drop in hemoglobin may be significant, it is advised that hemoglobin or hematocrit be obtained pretreatment and at week 2 and week 4 of therapy or more frequently if clinically indicated. This has not been a factor in AML trials thus far. ²⁴

5.3.3.3 Hepatic Failure –this has been noted only in hepatitis C patients.

5.3.3.4 Other reported toxicities:

Pruritis

Severe acute hypersensitivity reactions.

Low calcium levels

Low magnesium levels

Serious skin reactions including vesiculobullous eruptions, reactions in the spectrum of Stevens-Johnson Syndrome (erythema multiforme major) with varying degrees of skin and mucosal involvement and exfoliative dermatitis (erythroderma) have been reported in patients receiving PEGASYS with and without ribavirin. Patients developing signs or symptoms of severe skin reactions must discontinue therapy.

Pulmonary Disorders

Dyspnea, pulmonary infiltrates, pneumonitis, pulmonary hypertension, and pneumonia have been reported during therapy with ribavirin and interferon.

Bone Marrow Suppression

Pancytopenia (marked decreases in RBCs, neutrophils and platelets) and bone marrow suppression have been reported in the literature to occur within 3 to 7 weeks after the concomitant administration of pegylated interferon/ribavirin and azathioprine. This has been reversible and is of less concern in patients with hematologic malignancies.

Pancreatitis

Ribavirin therapy should be suspended in patients with signs and symptoms of pancreatitis, and discontinued in patients with confirmed pancreatitis.

5.3.4 HOW SUPPLIED/STORAGE AND HANDLING

Ribavirin is available as tablets for oral administration. Each tablet contains 200 mg of ribavirin and is light pink to pink colored, flat, oval-shaped, film-coated, and engraved with RIB 200 on one side and ROCHE on the other side. They are packaged as bottle of 168 tablets (NDC 0004-0086-94).

5.3.5 Storage and Handling

The bottle is stored at 25°C (77°F); excursions are permitted between 15°C and 30°C (59°F and 86°F) [see USP Controlled Room Temperature]. Keep bottle tightly closed.

6.0 STUDY CALENDAR (Appendix 5)

Baseline evaluations are to be conducted within 1 week prior to the start of the protocol unless otherwise specified.

Before beginning the treatment protocol, each patient will have the following performed:

- Complete history and physical exam including: Demographics, past medical and surgical history, medications, allergies, vital signs, height, weight, systemic exam including neurological exam
- EKG and Chest x-ray
- Bone marrow aspirate/biopsy, cytogenetics, molecular diagnostic studies to assess for the
 presence of FLT-3 or NPM-1 mutations and flow cytometry within 2 weeks of treatment.
 If these studies were performed elsewhere, an aspirate only will be performed to obtain
 material to perform the baseline correlative studies that are part of the protocol. (See
 section 8).
- CBC with differential, platelet count
- Chemistry including complete liver function tests, BUN/Cr, LDH and other electrolytes
- Uric acid level
- Urine analysis and urine pregnancy test for female patients of childbearing potential
- DIC panel
- Peripheral blood for correlative studies (See section 8 and Appendix 5)

After the beginning of each cycle, each patient will have the following tests performed at the noted time points:

- CBC with differential and platelets twice per week
- Chemistry including liver function tests, BUN/Cr and other electrolytes twice weekly
- Triglycerides and cholesterol on Day 1 of each cycle for those on Arm A (rapamycin) only
- Abbreviated physical examination and assessment of performance status
- A bone marrow aspirate only will be performed on Day 10 or 11 of therapy after completion of the decitabine and before initiation of rapamycin or ribavirin in CYCLE 1 ONLY for correlative studies including the phosphorylation status of mTOR effectors and stem cell frequency.
- A trough rapamycin level (arm A only) will be drawn on day 14 and 21 of each cycle. A level will also be drawn on Day 1 of Cycle 2 to assure a subtherapeutic level when decitabine is started in subsequent cycles only if the level on Day 21 was elevated.
- A bone marrow aspirate and biopsy will be performed after the completion of cylces 1, 3, and at the end of the study. This may occur on Days 22 through 26 of the cycle.
- A marrow aspirate and biopsy will also be performed at time of suspected disease progression and at study completion or at any other time the treating physician deems important for disease status determination

7.0 MEASUREMENT OF EFFECT Responses will be assessed at the end of cycle 1 (for progression only) and cycle 3 and at study conclusion or patient withdrawal from study (See 8.2 below).

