4.1.1 Study schema

Note: Those patients with morphologic M4/M5 subtypes²⁸ will be treated on Arm B and all other subtypes on Arm A. At study entry, all patients will have samples procured for testing of eIF4E expression but this will not determine allocation to arm A or B which will be made solely on the basis of FAB subtype. M4 subtype is acute myelomonocytic leukemia and M5 acute monocytic leukemia.

- Decitabine (Arms A and B)
- 20mg/m2 will be given as an intravenous infusion daily for 10 consecutive days starting on day 1 of cycle 1.
- In subsequent cycles, decitabine will be given for 5 days (day 1-5)

Rapamycin (Arm A)

- o For non-M4/M5 AML cases²⁸
- A 6 mg loading dose will be administered on Day 11 in cycle 1 and day 6 in subsequent cycles. Thereafter, 2 mg/day will be administered per schedule below. This may be reduced to 1 mg/day if levels are elevated (>15 ng/mL).
- o Toxicities will be as defined in section 9 using NCI Common Toxicity Criteria for Adverse Events (CTCAE (version 4.0) Appendix 3)
- o Rapamycin will be given from day 11 to 22 in cycle 1 and on days 6 to 22 in subsequent cycles.

Dose Level	Rapamycin	Decitabine
Level -1	1 mg	20 mg/m2
Level 1	2 mg	20 mg/m2

The rapamycin dose for phase II of the study was chosen based on results from the phase I study (ULEU08049).

Ribavirin (Arm B)

For M4/M5 cases²⁸—These patient are anticipated to have high eIF4E expression as expressed by Western blotting²⁴.

In cycle 1, ribavirin will be dosed from Day 11 through Day 28.

In subsequent cycles, ribavirin will be started on Day 1 on a continuous basis until study completion. These doses were chosen based on those found effective and tolerated in previous studies²⁴.

Dose level cohorts are listed in the table below. Subject enrollment will start at **Dose Level 1** (1000 mg). Enrollment in subsequent dose levels (escalation to Dose level 2 and 3, or de-escalation to Level -1 and -2) will follow the dose escalation and dose de-escalation plans as outlined below.

ULEU-13049 14 Version date: 09Aug2017

Dose Level	Ribavirin	Decitabine	Description
Level -2	600 mg bid	20mg/m2	Dose de-escalation cohort
Level -1	800 mg bid	20mg/m2	Dose de-escalation cohort
Level 1	1000 mg bid	20mg/m2	Initial cohort
Level 2	1200 mg bid	20 mg/m2	Dose escalation cohort
Level 3	1400 mg bid	20mg/m2	Dose escalation cohort

Dose Escalation Plans for Ribavirin (Arm B)

Number of patients with DLT at a given dose level	Escalation Decision Rule

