4.5.1.3 Dose modification for toxic range rapamycin level

If the rapamycin level at the time of scheduled measurement is >15 ng/mL, the dose will be held for 5 days, and a repeat level will be drawn on the 5^{th} day. If the level is still >15, the drug will be held for 5 more days and the level repeated. Once the repeat level is no longer above the normal range, the daily dose will be reduced to 1 mg and a rapamycin level will be drawn 5 days after the dose adjustment has been made. If the level is again ≥ 15 ng/dL, drug will be held until levels return to the therapeutic range and then started again at 1 mg every other day.

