APPENDIX 5 (ARM A) Decitabine and Rapamycin

												D	ays											
Tests	Pre	1	2	3	4	5	6	7	8	9	10	11	12	13	14	15	16	17	18	19	20- 22	22-26	28	EOS
Decitabine		X	X	X	X	X	X ¹⁰	X ¹⁰	X ¹⁰	X10	X ¹⁰													
Rapamycin							X11	X11	X11	X11	X ¹¹	X	X	X	X	X	X	X	X	X	X			
History & Physical	X	x																						
CBC w/diff & plts	X	X						X^3																
Chemistries	X	X8						X^3																
LDH	X					X		X^3																
Urate	x	x						X ⁴																
Bone marrow	X										X1												X1	X1
Flow Cytometry	X																					X		
Cytogenetic Studies	X																					X		
DIC Panel	x																							
Molecular Studies ¹⁴	X																							
Bone marrow for Correlative Studies	X ⁵ 40cc										X540cc											X540cc		
Blood for correlative studies	X ⁷ 10cc										X ⁷ 10cc											X ⁷ 10cc		
EKG/CXR	X																							
U/A, PT, PTT, Pregnancy	X																							
Chimerism	X^2																						X^2	
Rapamycin Levels		X12													X9						X ⁹			
Evaluation of Response																							X ⁶	X ⁶
Long Term Follow Up																								X ¹³

- 1. Aspirate only in cycle 1 on day 10-11 and biopsy and aspirate at days 22-26 of cycles 1 and 3 for disease assessment, and at end of study. Marrows may also be performed when clinically indicated at other times for disease assessment. Substitute peripheral blood if aspirate/marrow cannot be obtained.
- In those patients who have had an allogeneic transplant by chromosome (sex mismatched transplants) or by PCR assay. This can be done on either blood or marrow at physicians' choice.
- 3. Twice per week or as clinically indicated
- 4. As indicated clinically
- 5. 40 cc aspirate in green top (heparinized) tubes; if marrow is a dry tap, substitute 40 cc blood total
- 6. Cycles 1 and 3 only and at end of study or study discontinuation.

- 7. 10cc in green top tube.
- 8. Include cholesterol and triglycerides on day 1 of each cycle only.
- Rapamycin levels will be drawn (trough) on days 14 and 21. Patients will be asked to hold the daily dose until the level is drawn.
- 10. Decitabine is given on days 1-10 during cycle 1. In subsequent cycles, decitabine is given days 1-5.
- 11. Rapamycin starts on Day 6 starting with Cycle 2
- 12. Cycle 2 Day 1 only
- 13. Every 6 months for up to 2 years after date of last treatment
- 14. Molecular studies completed previously are acceptable if results are in the medical record.

Version date: 09Aug2017

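### A rapamycin level above 15 ng/mL cuts the daily dose to 1 mg, but the 6 mg load on day 6 of every later cycle is left in place

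*Combined protocol and SAP*

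**What the plan says.** Section 4.1.1 sets the load for Arm A: "A 6 mg loading dose will be administered on Day 11 in cycle 1 and day 6 in subsequent cycles". It then sets the daily dose: "Thereafter, 2 mg/day will be administered per schedule below. This may be reduced to 1 mg/day if levels are elevated (>15 ng/mL"). Dosing days are also fixed there: "Rapamycin will be given from day 11 to 22 in cycle 1 and on days 6 to 22 in subsequent cycles".

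Section 4.5.1.3 applies when a scheduled level is above 15 ng/mL. Rapamycin is held for 5 days and the level repeated. Once the repeat is acceptable, "the daily dose will be reduced to 1 mg and a rapamycin level will be drawn 5 days after the dose adjustment". If that level is high again, the drug is held and restarted at 1 mg every other day. The load is not mentioned at either step.

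Routine monitoring is in Appendix 5 (Arm A), footnote 9: "Rapamycin levels will be drawn (trough) on days 14 and 21". Section 6.0 adds one conditional draw: "A level will also be drawn on Day 1 of Cycle 2 to assure a subtherapeutic level when decitabine is started in subsequent cycles", and this "only if the level on Day 21 was elevated". Footnote 12 limits it: "Cycle 2 Day 1 only".

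**The concern.** The dose cut and the load are written as separate instructions, and only the daily dose is cut. A site that follows the text exactly gives a patient whose level was in the range 4.5.1.3 calls toxic a first dose six times the new daily dose, at the start of every later cycle. The same holds for a patient reduced to 1 mg every other day.

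The load acts on days 6 to 10, before the first routine trough of the cycle on day 14. The scheduled levels could therefore look satisfactory in a patient who has been back above the protocol's own limit. Section 5.2.2 relies on frequent level monitoring when it permits drugs that interact through CYP3A4, so the timing of that monitoring matters.

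**Working it through.** The plan gives no figure to reproduce. The check follows one patient through the rules as written.

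**Inputs from the protocol.** Half-life 62 h (section 5.2). Cycle 1: 6 mg on day 11, then 2 mg daily (4.1.1). Trough on day 14 above 15 ng/mL: hold 5 days, then 1 mg daily (4.5.1.3). Dosing ends on day 22. The next cycle starts on day 29, so its day 6 is day 34.

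**Assumptions.** One compartment, levels proportional to the amount in the body, clearance constant, day 14 dose withheld, 1 mg restarted on day 19. Half-lives of 46 and 93 h are assumed as a range.

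**The trigger.** r = 2^(-24/62) = 0.7647 is the fraction kept per day. Day 14 pre-dose amount = 6r³ + 2r² + 2r = 5.38 mg. Later amounts are divided by this.

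**The rest of cycle 1.**
- Repeat on day 18 or 19: r⁴ = 34% or r⁵ = 26%.
- Day 21: (5.38r⁷ + r² + r)/5.38 = 40%.
- Day 24, the recheck 5 days after the 1 mg restart: (5.38r¹⁰ + r⁵ + r⁴ + r³ + r²)/5.38 = 37%.

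From a day 14 level of 23 ng/mL the highest of these is 0.40 × 23 = 9.2 ng/mL. Every check passes. Day 21 is not elevated, so the Day 1 draw in section 6.0 is not ordered.

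**The next cycle.** Residual on day 6 = 5.38r²⁰ + r¹⁵ + r¹⁴ + r¹³ + r¹² = 0.137 mg. Day 7 with the load = (6 + 0.137)r = 4.69 mg. Day 7 with 1 mg instead = (1 + 0.137)r = 0.87 mg. Each later day is (previous + 1)r.

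| Day of next cycle | With 6 mg load | With 1 mg instead |
|---|---|---|
| 7 | 87% | 16% |
| 8 | 81% | 27% |
| 9 | 76% | 35% |
| 10 | 72% | 41% |
| 11 | 70% | 45% |
| 14 | 65% | 54% |

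Percentages are of the cycle 1 day 14 level.

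**Limits.** Day 7 is above 15 again if day 14 exceeded 15/0.872 = 17.2 ng/mL. The next day 14 trough shows it only if the earlier level exceeded 15/0.645 = 23.3 ng/mL. From 20 ng/mL with the load, the levels on days 7 to 11 are 17.4, 16.2, 15.2, 14.5 and 13.9, and day 14 is 12.9. The excess lasts about three days and is not seen.

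**Sensitivity to half-life**, same formulas:

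| Half-life | r | Day 14 amount | Day 7 with load | Over 15 if day 14 above | Missed on next day 14 up to |
|---|---|---|---|---|---|
| 46 h | 0.6965 | 4.39 mg | 95.7% | 15.7 ng/mL | 26.9 ng/mL |
| 62 h | 0.7647 | 5.38 mg | 87.2% | 17.2 ng/mL | 23.3 ng/mL |
| 93 h | 0.8362 | 6.58 mg | 83.2% | 18.0 ng/mL | 18.9 ng/mL |

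(Next day 14: 55.7%, 64.5% and 79.2%.)

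**A check that does not need the patient's history.** The steady-state amount just after a dose is 1/(1 - r) = 4.25 mg on 1 mg daily and 1/(1 - r²) = 2.41 mg on 1 mg every other day. The 6 mg load is 6/4.25 = 1.41 times the first and 6/2.41 = 2.49 times the second.

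**The case against.** The strongest objection concerns which patient is at risk. A reader might infer that the problem lies with an elevated day 21 level, say above 20 ng/mL. The monitoring rules do not support that. On uninterrupted 2 mg dosing the day 21 amount is 6.33 mg, so day 14 is 5.38/6.33 = 85% of it. Any day 21 level above 15/0.85 = 17.6 ng/mL would already have triggered the hold on day 14. The calculation above therefore follows the patient caught on day 14, for whom the harm remains.

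A reader might also infer that the Day 1 draw, which has no number for a subtherapeutic level and no stated action, lets decitabine start on top of substantial rapamycin. That is a gap in detail with little effect. At 62 h the Day 1 level is 12% of day 21 if the day 21 and 22 doses are withheld and 20% if both are taken, or 1.8 to 3.0 ng/mL from 15. The documents do not call an overlap harmful. They give no basis for delaying decitabine, and section 4.1.1.1 lets a 28-day cycle stretch only to 30 days.

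Two further points stand in part. Section 4.5.4 lets the physician adjust doses, so many would omit the load unprompted; the result is uneven handling rather than certain error. The 5-day recheck can be read as counted from the first reduced dose, but for this patient that falls in cycle 1, not at the restart. Finally, the load serves a purpose in a short dosing window, and leaving it out slows the rise.

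**Conclusion.** The point holds for the load. As written, a level-driven cut leaves the 6 mg load in every later cycle. At 62 h this takes a patient whose cycle 1 day 14 level was above about 17 ng/mL (15.7 to 18.0 across the assumed half-lives) back over 15 ng/mL on day 7 of the next cycle. Routine sampling would miss it up to about 23 ng/mL. The missed band is wide at 46 h and narrow at 93 h. Patients only just above 15 ng/mL on day 14 stay below it at 62 h even with the load.

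The size rests on a simple model with constant clearance and proportional levels; the textual gap does not. How many patients would be affected cannot be derived from the documents. It would be wrong to infer that the efficacy conclusion is at risk: the primary endpoint, sample size and Simon rule are unaffected. This is a low-cost safety clarification worth making.

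**What to change.** Add to sections 4.1.1 and 4.5.1.3: *No loading dose is given while a patient is on a reduced rapamycin dose. Rapamycin restarts on day 6 at the reduced dose, and the 5-day recheck is drawn 5 days after the first reduced dose is taken.* As worded, this also covers patients reduced for toxicity under 4.5.1.1, where the load is not mentioned either.

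Optionally, extend the Day 1 level in section 6.0 and footnote 12 to any cycle that follows a day 21 level above 15 ng/mL, to match its stated purpose. That adds at most one level per elevated day 21 result.

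The cost is a slower return to therapeutic levels: by day 11 about 45% rather than 70% of the earlier day 14 level (from 20 ng/mL, 9.1 rather than 13.9). Nothing in the analysis changes.

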7.1 Definitions

- 7.1.1 Complete remission: Normocellular marrow (>20%) with < 5% blasts and no extramedullary leukemia. Absence of dysplasia. Normal peripheral blood counts ANC>1000 and platelets > 100,000. Patients with these criteria and persistently abnormal cytogenetics will be judged as complete remission, but these aberrations will be noted.
- 7.1.2 Partial remission: Normocellular marrow (>20%) with 5-20% blasts and no extramedullary leukemia.
- 7.1.3 Treatment failure: failure to achieve CR or PR.
- 7.1.4 Stable disease: No change in percentage of marrow blasts.
- 7.1.5 Relapse: The reappearance of circulating blast cells of the malignant phenotype; > 5% blasts in the bone marrow not attributable to another cause; and/or, the development of extramedullary leukemia.
- 7.1.6 Hematologic recovery: ANC \geq 1500 for 3 consecutive days; non-transfused platelets \geq 100; no leukemic blasts in the peripheral blood.
- 7.1.7 Duration of remission/response: defined as the time from documented remission/response to the time of progression.
- 7.2 Confirmatory Measurement/Duration of Response
 - 7.2.1 A bone marrow biopsy and aspirate will be obtained after cycle 3 and after each cycle and at the end of study at which time determination of a PR or CR will be made.
 - 7.2.2 Duration of overall response

The duration of overall response is measured from the time measurement criteria are met for CR or PR until the first date that recurrent or progressive disease is objectively documented.

The duration of CR is measured from the time measurement criteria are first met for CR until the first date that recurrent disease is objectively documented. Note will be made of use of maintenance decitabine.

- 7.2.3 Progression-Free Survival PFS is defined as the duration of time from start of treatment to time of progression.
- 7.2.4 Response Review

All bone marrow biopsies and aspirates will be reviewed by a hematopathologist.

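### Partial remission has no baseline comparison and overlaps stable disease, CRp is undefined, and section 11 does not say which categories count in the 3-of-9 and 10-of-24 rules

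*Combined protocol and SAP*

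**What the plan says.** **Response categories (7.1).** PR in 7.1.2 is "Partial remission: Normocellular marrow (>20%) with 5-20% blasts and no extramedullary leukemia". Complete remission (CR) in 7.1.1 needs under 5% marrow blasts and, among other things, "Normal peripheral blood counts ANC>1000 and platelets > 100,000". 7.1.3 reads "Treatment failure: failure to achieve CR or PR" and 7.1.4 reads "Stable disease: No change in percentage of marrow blasts". Objective 1.1 lists CRp beside CR and PR, but section 7 does not mention it.

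**Decision rule (11.0).** Arm A stops if 2 or fewer of 9 evaluable patients respond. The null is rejected at 10 or more responses in 24. The null rate is 25%, from single-agent decitabine, and the alternative is 50%. The categories that make up a response are not listed. Section 11 also uses response as a yes/no variable in the exploratory correlative analysis.

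**Entry (3.1).** The refractory route after two induction cycles (3.1.3), relapse after CR (3.1.4) and relapse after transplantation (3.1.5) state no minimum blast percentage. The other refractory route, after one cycle, requires more than 40%.

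**Timing.** 7.0 says: "Responses will be assessed at the end of cycle 1 (for progression only) and cycle 3 and at study conclusion", or at withdrawal. Appendix 5 note 6 lists cycles 1 and 3 and end of study or discontinuation. 7.2.1 places the marrow "after cycle 3 and after each cycle and at the end of study at which time determination of a PR or CR" is made.

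**The concern.** A response category should separate patients whose disease receded from those whose disease did not. A band on the post-treatment blast percentage does this only if every patient starts above the band. Here some can start inside it, and for them PR can be met with no fall in blasts.

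CRp raises the opposite problem. A category that the objectives treat as efficacy has no definition, and 7.1.3 puts anyone without CR or PR among the failures.

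Both Simon decisions rest on a count of responses in 9 and then 24 patients. In samples this small, the classification of a single patient changes the error rates materially.

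**Working it through.** **1. Can a patient start inside the band?** Yes. The three routes above set no floor. Section 2.6 reports that the team's earlier phase I study, in relapsed or refractory AML, enrolled patients with 6% to 93% blasts (mean 35%). At least one of those 13 patients therefore began within 5-20%. This shows that such entry happens, not how often.

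**2. How is that patient scored?** Take 12% blasts at entry, a normocellular marrow and no extramedullary disease at assessment.

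| Marrow at assessment | PR (7.1.2) | Stable disease (7.1.4) |
|---|---|---|
| 12% (unchanged) | met | met |
| 18% (rise) | met | not met |

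The paragraph on number of cycles in 4.1.1.1 lists PR/CR and stable disease as separate outcomes after cycle 3. Both lead to continued treatment, so nothing in the conduct of the trial forces a choice between them. The only explicit progression criterion, in the same paragraph, is a doubling of peripheral blood blasts, so it does not remove the rising case. By contrast, section 2.4 describes PR in a cited single-agent rapamycin study as a fall of about half in blasts, which is relative to baseline.

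**3. Reproduce the design.** Inputs from section 11: n1 = 9, stop at 2 or fewer; n = 24, reject at 10 or more; rates 0.25 and 0.50. Write b(x; n, p) for the binomial probability.

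- Early termination = sum over x = 0 to 2 of b(x; 9, p). At 0.25: 0.0751 + 0.2253 + 0.3003 = 0.6007 (stated 60%).
- P(declare active) = sum over x = 3 to 9 of b(x; 9, p) × P(Bin(15, p) ≥ 10 − x). At 0.25: 0.0485 (stated limit .05). At 0.50: 0.8055 (stated 80%).

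**4. Effect of one reclassified patient (assumed; the documents give no shares).** For each pair (x1, x2) of responses in the 9 and the 15, pick one patient at random from those eligible to be reclassified, then apply the rule to the altered counts.

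- *Upward, true rate 0.25.* The non-responder scored PR is in stage 1 with probability (9 − x1)/(24 − x1 − x2). P(declare active) goes from 4.8% to 10.8%, and early termination from 60.1% to 48.4%.
- *Upward, milder model.* One fixed patient always scores PR and the other 23 respond at 25%. If that patient is in stage 1, the sum over x = 2 to 8 of b(x; 8, 0.25) × P(Bin(15, 0.25) ≥ 9 − x) is 0.0913. If in stage 2, the sum over x = 3 to 9 of b(x; 9, 0.25) × P(Bin(14, 0.25) ≥ 9 − x) is 0.0823. The average is (9 × 0.0913 + 15 × 0.0823)/24 = 0.086, or 8.6%.
- *Upward, as a share q of non-responders.* The scored rate is 0.25 + 0.75q. At q = 5% it is 0.2875 and P(declare active) is 10.9%; at q = 10% it is 0.325 and 20.4%.
- *Downward, true rate 0.50.* The responder scored as a failure is in stage 1 with probability x1/(x1 + x2). Power goes from 80.5% to 68.5%.

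**5. CRp.** Suppose that CRp means CR without platelet recovery; this is an assumption. That patient misses the platelet criterion in 7.1.1, falls below the 5% floor in 7.1.2, and is a treatment failure under 7.1.3.

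**6. Timing.** 7.0 and Appendix 5 note 6 name the same time points; 7.0 adds that cycle 1 is for progression only. The one conflict is the reference in 7.2.1 to a marrow after each cycle.

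**The case against.** **The response set is nearly settled.** 7.1.3, 7.2.1 and 7.2.2 all pair CR with PR; 7.2.2, for instance, has overall response "measured from the time measurement criteria are met for CR or PR". This stands in large part. What remains is that section 11 does not adopt that set, and that objective 1.1 adds CRp. It would go too far to say that the protocol gives no indication of what a response is.

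**An unchanged marrow is stable disease.** A reader might infer that the plan tells the investigator to count it as a response. It does not: the patient meets both definitions, and the fault is the missing precedence rule. Only a rise within the band meets PR without also meeting stable disease, and then only with a normocellular marrow and no extramedullary disease.

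**Expert review will sort this out.** 7.2.4 says "All bone marrow biopsies and aspirates will be reviewed by a hematopathologist". That secures the reading of each marrow but supplies no baseline comparison, which the written rule lacks.

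**Entry requires AML by WHO criteria (3.1.2).** That applies to every route. However, the protocol attaches no blast figure to it and does not say that it must be met afresh at relapse, and the phase I range begins at 6%.

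**The error rates are hypothetical.** This is correct. A reader might infer that the true type I error is 10.8%. The documents do not support that: they do not say how many patients are affected or which categories the 25% benchmark counts.

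**Conclusion.** The point holds as a defect of definition that should be fixed. As written, PR can be met without any fall in blasts, PR and stable disease can both apply to the same marrow, CRp has no definition, and section 11 leaves the counted set unstated. The design arithmetic is sound and is not in dispute.

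The size is illustrative. The upward figures (4.8% to 8.6% or 10.8% for one patient) assume that the 25% benchmark does not count such patients. The downward figure (80.5% to 68.5%) assumes that the 50% was meant to include the patient scored as a failure. Nothing in the documents shows which effect is larger, so the net direction of any bias is unknown. The CRp example rests on an assumed meaning and carries little weight beyond showing that a definition is needed. The effect on the correlative analysis is minor, since that analysis is called exploratory.

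The three timing passages might be read as mutually contradictory. They are not; only 7.2.1 departs from the other two.

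**What to change.** 1. **7.1.2:** require a pre-specified fall X from the pre-study marrow blast percentage, with X set by the sponsor, so that unchanged or rising blasts cannot be PR and PR and stable disease exclude each other. With the 5% floor kept, a baseline B can reach PR only if B(1 − X) ≥ 5, so baselines below 5/(1 − X) cannot score PR. For illustration only, that is 6.7% blasts at X = 25% and 10% at X = 50%. State how such patients are scored.
2. **7.1 and 7.2:** define CRp, say whether it counts as a response, and align 7.1.3 and 7.2 with that decision.
3. **Section 11:** list the categories counted in the 3-of-9 and 10-of-24 rules, and confirm that the 25% and 50% rates refer to the same set.
4. **7.2.1:** reconcile it with 7.0 and Appendix 5 note 6 on when a response is determined.

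**Cost.** This is wording plus a check of what the benchmark counts. No new procedure is needed: section 6.0 already requires a pre-study marrow, or a study aspirate when the work-up was done elsewhere. The protocol should say which reading is the baseline. The downside is that some patients with low baseline blasts would no longer count as PR. The cut-offs stand unless the benchmark counts a different set; in that case either the response set or the null and cut-offs must be restated.

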4.5.2 Decitabine

No specific dose modification for hematologic toxicities.

Schedule modifications will be based on disease status and count recovery from the previous cycle as follows:

Subjects with >5% blasts in marrow will proceed to a 5 day cycle.

Those with no morphological evidence of leukemia (<5% blasts)will receive a 5 day course of decitabine

Those with no evidence of AML but who have grade 4 neutropenia (<500/uL) of at least 14 days duration will receive 5 days with the next cycle. If this happens again in the subsequent cycle, 3 days will be administrated.

Subjects should receive 3 cycles of treatment as discussed above before treatment failure is determined in the absence of obviously resistant, progressive disease.

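### Sections 7.1.1 to 7.1.3 rank a cleared marrow that misses CR on dysplasia or counts below one with 5-20% blasts; CRp is undefined, and section 11.0 does not say what counts as a response

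*Combined protocol and SAP*

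**What the plan says.** Section 7.1 defines three categories that together classify every assessed patient.

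- CR (7.1.1): "Complete remission: Normocellular marrow (>20%) with < 5% blasts and no extramedullary leukemia", and in addition "Absence of dysplasia. Normal peripheral blood counts ANC>1000 and platelets > 100,000".
- PR (7.1.2): "Normocellular marrow (>20%) with 5-20% blasts and no extramedullary leukemia". It carries no dysplasia or blood-count condition.
- Failure (7.1.3): "Treatment failure: failure to achieve CR or PR".

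Sections 7.2.1 and 7.2.2 also name only CR and PR when they date and determine response. Objective 1.1, in both the synopsis and section 1.0, lists CRp between CR and PR as an Arm A efficacy measure, but section 7 contains no definition of it.

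Section 11.0 tests a response rate in a Simon two-stage design. Arm A stops if 2 or fewer of 9 respond, and the null of 25% is rejected with 10 or more of 24. It does not list the categories that count as a response.

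Section 4.5.2 treats under 5% blasts as no morphological leukemia and gives a schedule rule for "Those with no evidence of AML but who have grade 4 neutropenia" lasting at least 14 days.

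**The concern.** Response categories should be ordered so that, with everything else equal, fewer marrow blasts never give a worse class. Here they can. The PR definition has a floor of 5% blasts, and CR adds conditions that PR does not have. A marrow that clears below 5% but keeps dysplasia or low counts falls between the two and lands in 7.1.3.

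The state is plausible in this trial. Section 4.5.2 provides for cleared patients with prolonged neutropenia, and section 4.5.1.2 anticipates that all patients may become pancytopenic. Section 4.1.1.1 allows the cycle 3 marrow on days 22 to 26, without waiting for count recovery.

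Response is the only Arm A endpoint with a decision rule. If section 11.0 is applied with the section 7 categories, some cleared marrows would count against activity. With 9 patients in the first stage, one reclassified patient can decide whether the arm continues. The same yes/no response also feeds the chi-square correlative analysis in section 11.0.

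**Working it through.** **1. Classification.** Apply 7.1.1, 7.1.2 and 7.1.3 in order. All rows assume a normocellular marrow (>20%) and no extramedullary leukemia.

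| Marrow blasts | Dysplasia | Counts | CR? | PR? | Class |
|---|---|---|---|---|---|
| <5% | none | ANC >1000, platelets >100,000 | yes | – | CR |
| <5% | present | any | no | no, below the 5% floor | treatment failure |
| <5% | none | ANC ≤1000 or platelets ≤100,000 | no | no, below the 5% floor | treatment failure |
| 5-20% | any | any | no | yes | PR |

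Take two such patients with ANC 800. At 15% blasts the patient is a PR, and at 2% a treatment failure.

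**2. The plan's own figures.** Inputs from section 11.0: p0 = 0.25, p1 = 0.50, stop if ≤2 of 9, reject if ≥10 of 24, 15 patients in stage 2.

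- Early stop: P(X1 ≤ 2), with X1 ~ Bin(9, p).
- Rejection: sum over x1 = 3 to 9 of P(X1 = x1) × P(Bin(15, p) ≥ 10 − x1).

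At p = 0.25 the early-stop probability is 0.0751 + 0.2253 + 0.3003 = 0.6007 (stated 60%), and the type I error is 0.0485 (stated level .05).

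At p = 0.50 the early-stop probability is (1 + 9 + 36)/512 = 0.0898. Power is 0.1142 + 0.2090 + 0.2315 + 0.1612 + 0.0700 + 0.0176 + 0.0020 = 0.8055 (stated 80%).

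The stated design reproduces. The defect lies in what is counted against its thresholds.

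**3. Illustration of size.** The documents do not give the share s of true responders who clear the marrow but miss CR on dysplasia or counts, so s is assumed. If they are scored as failures at a true 50% rate, the counted rate is 0.50 × (1 − s).

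| s (assumed) | Counted rate | Power | Stage-1 stop |
|---|---|---|---|
| 0% | 50% | 80.5% | 9.0% |
| 10% | 45% | 65.6% | 15.0% |
| 20% | 40% | 47.0% | 23.2% |
| 30% | 35% | 28.4% | 33.7% |

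**4. The other direction.** If the response set is widened while the null stays at 25%, and the added patients raise the true null rate by 5 points to 30%, the rejection probability goes from 4.8% to 13.7%. At 10 points (35%) it is 28.4%.

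**The case against.** The best defence is that objective 1.1 names CRp, so the authors meant to credit some incomplete recoveries, and section 11.0 never equates response with CR plus PR. This stands in part. A reader might infer that the Simon count is certain to score these patients as failures, but section 11.0 leaves that open. It does not repair the definitions: CRp has no criteria, and 7.1.3, 7.2.1 and 7.2.2 leave it out.

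A reader might also assume that CRp could cover only low platelets. The documents never define it, so how much of the gap it would close cannot be judged from them.

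The section 4.5.2 rule concerns the schedule, not response. It is silent on dysplasia and gives no frequency. The same section normally wants three cycles before failure is declared, and section 7.0 assesses response again at study end or withdrawal, so a patient with low counts at cycle 3 may meet CR later. That lowers the number finally misclassified but does not remove the inversion.

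The power loss also assumes that the 50% design rate includes these patients. If 25% and 50% were both set on CR plus PR as written, power stays at 80.5%.

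**Conclusion.** The point stands as a fault in the stated definitions. Read literally, 7.1.1 to 7.1.3 turn a PR into a treatment failure when blasts fall below 5% and dysplasia or counts still bar CR. The undefined CRp and the unspecified response rate in section 11.0 leave no rule that corrects it.

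The size is unknown. The power range of 65.6% to 28.4% rests on assumed shares of 10% to 30% and on a 50% rate that includes the affected patients.

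Two stronger readings are not supported. One is that the endpoint fails to measure activity: full CRs, marrows with 5-20% blasts that meet PR, and clear failures are classified in the expected order, and only the cleared-but-incomplete group is misplaced. The other is that any marrow with 20% blasts is a responder: it must also be normocellular and free of extramedullary leukemia.

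**What to change.** - **Section 7.1:** define CRp. Add a category for the remaining normocellular (>20%) marrows with <5% blasts and no extramedullary leukemia that miss CR on dysplasia or counts. Rank both no worse than PR. Keep the cellularity condition, so that a hypocellular marrow with few blasts is not credited.
- **Section 7.1.3:** define failure as not achieving CR, CRp, the added category or PR. This stays exhaustive, so extramedullary disease and a hypocellular marrow with 5-20% blasts remain failures.
- **Sections 7.2.1 and 7.2.2:** name the same categories.
- **Section 11.0:** state which categories count toward 3/9 and 10/24, and confirm that the 25% null uses the same definition. Report the count with and without the added category.

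The cost is a few sentences. Marrow examinations, reviewed by a hematopathologist, and twice-weekly blood counts are already in the plan. The risk is a more inclusive count set against an unmatched null (step 4 of the working), so the null must be checked before the wider set is used for the decision.
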